12.6 Sample Size

12.6.1 Accrual estimates

100 participants will be recruited prospectively. Ample time has been allotted for patient recruitment. In the unlikely event that there is difficulty in recruiting a sufficient number of patients at Stanford Hospital, additional recruitment efforts at affiliated Stanford sites will be considered, if approved.

12.6.2 Sample size justification

The risk of lymphedema development is considered to be 30% in the surgical control group (group A), and studies have shown it is to be reduced to 4% when LYMPHA is applied during an axillary lymphadenectomy [12, 30]. With N=40 subjects (20 subjects per arm A and C) in the first stage, the power to stop after the first stage is 56%. Finally, with additional N=40 subjects (20 subjects per arm A and C) in the second stage, the overall power to stop at either the first or the second stage is 88%.

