SECONDARY OBJECTIVE(S)	To determine if the use of LYMPHA in breast cancer patient undergoing axillary lymphadenectomy will reduce the risk of limb lymphedema as measured by other metrics of clinical lymphedema, including limb volume, skin thickness measurements, and bioimpedance spectroscopy. To determine if the use of LYMPHA in breast cancer patients undergoing axillary lymphadenectomy will improve quality of life, as measured by limb-lymphedema-specific quality of life (LYMQOL) tool.
TREATMENT SUMMARY	Patients undergoing unilateral axillary lymphadenectomy will undergo the immediate lymphatic reconstruction (LYMPHA) at the same time.
SAMPLE SIZE	100 patients (randomized)
STATISTICAL CONSIDERATIONS	Fisher's exact test and general linear mixed models

A Randomized Clinical Trial of the LYMPHA procedure for the Prevention of Lymphedema after Axillary Lymphadenectomy

SCHEMA

Key:

LYMQOL = limb-lymphedema-specific quality of life
LYMPHA = LYmphatic Microsurgical Preventive Healing Approach

A Randomized Clinical Trial of the LYMPHA procedure for the Prevention of Lymphedema after Axillary Lymphadenectomy

LIST OF ABBREVIATIONS AND DEFINITION OF TERMS

LYMQOL	limb-lymphedema-specific quality of life
LYMPHA	LYmphatic Microsurgical Preventive Healing Approach
ICG	Indocyanine Green
ALND	Axillary Lymph Node Dissection

A Randomized Clinical Trial of the LYMPHA procedure for the Prevention of Lymphedema after Axillary Lymphadenectomy

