2.4 Study Design

We propose a randomized clinical trial to determine the efficacy of the LYMPHA procedure in breast cancer patients undergoing axillary lymphadenectomy.

Up to 100 subjects will be enrolled in the trial; they will undergo either lymphadenectomy, lymphadenectomy with soft tissue reinforcement (STR) or lymphadenectomy with LYMPHA. Subjects must meet all additional defined inclusion and exclusion criteria.

Please note that soft tissue reinforcement is common practice and used as the standard of care in some lymphedema centers. The addition of this group is important because it allows a comparison of LYMPHA to a currently commonly practiced alternative and the ability to assess for superiority of the LYMPHA procedure. In short, at Stanford, we perform soft tissue reinforcement with collagen scaffolding commonly and would like to start including these patients in our prospective analysis/study.

All patients that are enrolled will be randomized into one of three groups: Group A (surgical control group 1) – the patients will undergo lymphadenectomy alone with simple wound closure, Group B (surgical control group 2) – the patients will undergo lymphadenectomy with soft tissue reinforcement using a collagen scaffold, or Group C (treatment group) - the patients will undergo lymphadenectomy and LYMPHA at the time of wound closure as an adjunct to lymphadenectomy procedure.

Randomization will occur after it has been determined that patients are eligible for the trial intraoperatively. Patients are deemed eligible for the trial intraoperatively if ALND is performed and there are available lymphatics to bypass.

The study will be double blind and randomized. Each patient will be randomized to either the treatment or control group 1 or 2 and will be blinded to their group. While the surgeons will not be blinded, all personnel who track outcomes in clinic will be blinded. The primary outcomes that the protocol is designed to evaluate include efficacy, safety, and impact on the quality of life.

The study was started with 2-arm design (Group A and Group C). A preliminary assessment to the trial effects will be conducted using the current collected data. After the revised protocol is approved, the study will recruit subjects in the new 3-arm phase: 90 subjects (30 subjects per arm in the three groups (Groups A, B, C)

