3.4 Randomization Procedures

Since this study was started with two groups (A and C), and randomized 13 patients to the control group A and 14 patients to the treatment group C. However, 7 of the 14 patients that were randomized to treatment group C did not receive LYMPHA surgery , were considered screen fails. 27 patients will be used in intent-to-treat (ITT) analysis, however, 7 screen fails will not be counted in the per protocol (PP) analysis. In the new 3-arm phase, the randomization procedures will happen during ALND surgery time. and 90 subjects will be allocated in a 1:1:1 randomization ratio into three groups. The clinic staff obtaining measurements will be blinded to the treatment group

A Randomized Clinical Trial of the LYMPHA procedure for the Prevention of Lymphedema after Axillary Lymphadenectomy

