12. STATISTICAL CONSIDERATIONS

12.1 Statistical Design

The objectives of the study are to assess the efficacy of the LYMPHA procedure when compared to the results of wound closure alone and wound closure with soft tissue reinforcement in similar clinical cohorts. We plan to enroll a total of 100 patients in this randomized parallel clinical trial.

The hypothesis to be tested is that adjunctive surgical use of LYMPHA with an axillary lymphadenectomy will produce a superior effect in terms of lymphedema prevention when compared to the effect of an axillary lymphadenectomy alone and an axillary Axillary lymphadenectomy with STR. The primary endpoint, incidence of lymphedema at month 12, will be compared between LYMPHA and the control, axillary lymphadenectomy alone arm using a significance level of 5%.

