12.1.1 Randomization

Since this study was started with two groups (A and C), and randomized 13 patients to the control group A and 14 patients to the treatment group C. However, 7 of the 14 patients that were randomized to treatment group C did not receive LYMPHA surgery, were considered screen fails, Therefore in the preliminary assessment, 27 patients will be used in intent-to-treat (ITT) analysis, however, 7 screen fails will not be counted in the per protocol (PP) analysis. In the new 3-arm phase, the randomization procedures will happen during ALND surgery time. and 90 subjects will be allocated in a 1:1:1 randomization into three groups. The clinic staff obtaining measurements will be blinded to the treatment group.

A Randomized Clinical Trial of the LYMPHA procedure for the Prevention of Lymphedema after Axillary Lymphadenectomy

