12.2 Preliminary assessment

Since the study has stopped 2-arm recruitment and will start the new 3-arm recruitment, the current collected 2-arm data will be used to conduct a preliminary assessment, to check the comparability, safety and efficacy of the trial.

Preliminary assessment will evaluate the primary endpoint (presence of lymphedema) and secondary endpoints (skin thickness, BIS, and LYMPQOL). Both intent-to-treat (ITT) analysis and per protocol (PP) analysis will be explored.

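### The protocol's only power figure (88%) belongs to a two-stage, 40-per-arm design that is no longer run; 30 per arm gives about 69% for C vs A, and the stated total of 100 does not match 90 + 27 = 117

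*Protocol*

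**What the plan says.** Section 12.6.2 assumes a lymphedema risk of 30% in Group A and 4% with LYMPHA. It plans 20 patients per arm in A and C at a first stage, with 56% power to stop there, and 20 more per arm at a second, and concludes that "the overall power to stop at either the first or the second stage is 88"%. No other power figure appears in the protocol.

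The design described elsewhere is different:

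- Section 2.4: "the study will recruit subjects in the new 3-arm phase: 90 subjects (30 subjects per arm in the three groups".
- Section 3.4: "90 subjects will be allocated in a 1:1:1 randomization ratio into three groups". Section 12.1.1 repeats this.
- Section 12.2 (Preliminary assessment): "the study has stopped 2-arm recruitment and will start the new 3-arm recruitment".
- Sections 3.4 and 12.1.1: the two-arm phase randomised 13 patients to A and 14 to C, and 7 of those 14 did not receive LYMPHA. Section 12.1.1 adds that "in the preliminary assessment, 27 patients will be used in intent-to-treat (ITT) analysis".
- Sections 12.1 and 12.4.2: the test is Fisher's exact test at the 5% level. Sidedness is not stated.

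On the total, section 2.4 says "Up to 100 subjects will be enrolled in the trial" and section 12.1 says "We plan to enroll a total of 100 patients in this randomized parallel clinical trial". The synopsis and section 12.6.1 also give 100.

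**The concern.** The power statement describes a trial with two arms, two looks and 40 patients per arm in A and C. The trial now being run has three arms, 30 new patients per arm and, as far as the protocol shows, one final look. The first stage of 20 per arm was never completed. The preliminary assessment of the 27 two-arm patients has no stopping rule, and the reference on group sequential futility boundaries (number 31) is not cited anywhere in the text.

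A reader, ethics board or monitoring committee would take 88% as the power of the present trial. If the true figure is nearer 69%, the chance of missing the planned effect is 31% rather than 12%, and a non-significant C vs A result would be read with more confidence than it deserves. The target enrolment is also unclear, because 100 does not agree with the numbers already randomised and still to be randomised.

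**Working it through.** **Inputs.** Risks 30% (A) and 4% (C), and stages of 20 + 20 per arm, from 12.6.2. Level 5% from 12.1. Fisher's exact test from 12.4.2. Thirty per arm from 2.4. Counts of 13, 14 and 7 from 12.1.1. Two-sided testing and no dropout are assumptions, because the protocol states neither.

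**1. The protocol's own figures.** Take a two-look z test with unpooled variance and the Pocock boundary of 2.178 at both looks (two-sided 5%). The boundary is inferred, since 12.6.2 names none.

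- Drift at look k = (0.30 − 0.04) / √[(0.30×0.70 + 0.04×0.96)/n]
- n = 20: 0.26 / √(0.2484/20) = 2.333
- n = 40: 0.26 / √(0.2484/40) = 3.299
- Look 1: P(Z > 2.178 − 2.333) = 56.2%
- Either look, bivariate normal with correlation √0.5: 88.2%

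Both match the stated 56% and 88%. An O'Brien-Fleming boundary gives 32.1% and 90.8%, which does not match. The arithmetic is therefore sound for the design it describes.

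**2. The current design, new patients only.** Power = Σ P(a)·P(c) over all tables with Fisher p ≤ 0.05, where a ~ Bin(n, 0.30) and c ~ Bin(n, 0.04).

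| n per arm | Two-sided power |
|---|---|
| 30 | 68.9% |
| 40 | 86.9% |
| 41 | 88.0% |

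One-sided at 5%, 30 per arm gives 79.6%. The two-sided risk of a miss at 30 per arm is 100 − 68.9 = 31.1%.

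**3. With the 27 earlier patients pooled, intention to treat.** A = 30 + 13 = 43 and C = 30 + 14 = 44. Group C events are Bin(37, 0.04) + Bin(7, r), where r is the risk in the 7 who did not receive LYMPHA.

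| r | Two-sided power |
|---|---|
| 4% | 93.0% |
| 10% | 89.4% |
| 20% | 82.2% |
| 30% | 73.7% |

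**4. The total.** Randomised already plus planned: 13 + 14 + 90 = 117, which is 17 more than 100. Leaving out the 7 called screen fails gives 117 − 7 = 110. If 100 were a firm ceiling, 100 − 27 = 73 places would remain, about 24 per arm instead of 30. If 100 meant new patients only, it would still not be 90.

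**The case against.** The best case for the protocol is that the 27 patients may belong in the final analysis. Section 12.4.1 puts all participants in the intention-to-treat set. Section 12.5.2 says the primary analysis uses everyone enrolled and assigned. Section 3.4 mentions the intention-to-treat use of the 27 without limiting it to the preliminary assessment. On that reading 69% is the lowest of several possible figures. Moreover, removing the 7 untreated Group C patients leaves 43 in A and 37 in C. That is 80 in all, as in 12.6.2, with a single-look two-sided Fisher power of 87.8%.

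Part of this stands. Pooling is an open reading, and some pooled figures exceed 88%. But 43 vs 37 is a per-protocol set, not the intention-to-treat primary, and the protocol never links it to the power statement. Under intention to treat the figure falls to 73.7% if the 7 carry the control risk.

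A second objection is that setting 88% against 69% mixes a normal approximation with an exact test. That is fair as to size: the normal approximation at 30 per arm gives 77.9% two-sided. The shortfall does not vanish on a common basis, though. Fisher's test falls from 86.9% at 40 per arm to 68.9% at 30, a loss of 18 points.

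Third, the total could be counted as 110 if the 7 are removed under section 4.2. That does not match 100 either, and 117 is the number randomised.

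**Conclusion.** The concern holds. The 88% is not miscalculated; it is attached to a design that the protocol has replaced, and no power is given for the design now in force. For the 90 new patients, C vs A by Fisher's exact test has 68.9% power two-sided and 79.6% one-sided, at 30% vs 4%, level 5%, with no dropout. Any attrition lowers both. If the 27 are pooled under intention to treat, two-sided power runs from 73.7% to 93.0% for an assumed risk of 30% down to 4% in the 7 untreated Group C patients. No single figure can be settled until the protocol fixes who is analysed and the sidedness of the test. The total of 100 is inconsistent with 90, 110 and 117 alike. These figures concern C vs A only; whether C vs B is also primary is a separate question.

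**What to change.** 1. In 12.6.2, delete the first-stage and second-stage text and state power for one final look, with the sidedness. If the test is two-sided and only new patients count, the statement would be 69% power for Group C vs Group A with 30 per arm, 4% vs 30%, Fisher's exact test at 5%.
2. State whether the 27 two-arm patients enter the final primary analysis, and make 3.4, 12.1.1, 12.2, 12.4.1 and 12.5.2 agree. If they do enter, give the pooled intention-to-treat power (43 vs 44) together with the risk assumed for the 7 Group C patients who did not receive LYMPHA.
3. Give one total in the synopsis, 2.4, 12.1 and 12.6.1, for example 90 in the three-arm phase plus 27 in the two-arm phase, 117 in all.

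The cost is protocol wording and, for new patients alone, a less favourable stated power. It needs no patients beyond the 90 already planned and no change of test. If the sponsor wants 88% from the new patients alone, a single-look two-sided Fisher test would need 41 per arm, which is a separate decision.

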12.6.3 Effect size justification

The effect size used in the previous subsection was based on the study conducted by Boccardo et al, in which 74 patients underwent LYMPHA procedure after axillary lymph node dissection [12]. The incidence of lymphedema in the cited cohort after the LYMPHA procedure was 4.05%. Comparatively, the incidence of lymphedema after axillary lymph node dissection ranges from 13-65% [13-16]. This study provides a reasonable baseline for comparison to as it includes the same target population (women undergoing axillary lymphadenectomy related to breast cancer) and shows a substantially lower incidence of lymphedema compared to other literature.

12.7 Criteria for future studies

The criteria for success of the LYMPH procedure would include: the metrics of lymphedema (limb volume, skin thickness, bioimpedance spectroscopy, lymphatic pattern) and quality of life will be improved compared to the control group ($p<0.05$). Additionally, the complication rate after the LYMPHA procedure will be comparable or less than axillary lymphadenectomy alone ($p<0.05$).

A Randomized Clinical Trial of the LYMPHA procedure for the Prevention of Lymphedema after Axillary Lymphadenectomy

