12.4.2 Analysis Plan

Fisher's exact tests will be used to determine significance of differences in lymphedema rates between LYMPHA and the lymphadenectomy alone control arm, and significance of differences in lymphedema rates between LYMPHA and the lymphadenectomy with STR control arm. If treatment arms differ significantly at baseline in demographics (for e.g. age), lymphedema status at the end of treatment will be compared between treatment groups via a logistic regression, using the necessary covariates. Depending on the attrition rate, we may also use mixed effects logistic regression models to determine whether the treatment arms significantly differ in the binary endpoint (lymphedema status). Mixed models automatically handle missing data, producing unbiased estimates as long as observations are missing at random. This allows the use of all available data from all subjects, thereby minimizing the effects of loss to follow-up.

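### The safety success criterion in section 12.7 is unworkable as written: it attaches p<0.05 to a comparable-or-lower complication rate and gives no margin

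*Protocol*

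**What the plan says.** Section 12.7 (Criteria for future studies) lists what success of the procedure would include. The safety element is that "the complication rate after the LYMPHA procedure will be comparable or less than axillary lymphadenectomy alone", with p<0.05 in brackets after it.

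Section 2.4 (Study Design) gives safety some standing: "The primary outcomes that the protocol is designed to evaluate include efficacy, safety, and impact on the quality of life".

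The rest of the statistical text concerns lymphedema and the secondary efficacy measures:

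- Section 12.1 sets its 5% significance level for the incidence of lymphedema at month 12, LYMPHA against lymphadenectomy alone.
- Section 12.4.2 states that "Fisher's exact tests will be used to determine significance of differences in lymphedema rates". No test is named for complications.
- Section 12.6.2 gives power for lymphedema only.
- No margin, null hypothesis, expected rate or sample size for complications appears anywhere in the protocol. Section 7.1 says only that the potential for risk is deemed low.

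The numbers per arm are also stated in more than one way. Section 2.4 plans "90 subjects (30 subjects per arm in the three groups (Groups A, B, C" for the three-arm phase. Section 12.6.2 works with two stages of 20 per arm in A and C, hence 40 per arm. Section 3.4 adds the two-arm phase, which "randomized 13 patients to the control group A and 14 patients to the treatment group C".

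**The concern.** A p-value below 0.05 from a test of difference is evidence that two rates differ. A claim that they are comparable needs the opposite: evidence that any excess is smaller than some stated amount. With no such amount given, the p<0.05 in section 12.7 can be applied in two ways.

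1. **No significant increase counts as comparable.** Success then becomes easier the fewer patients there are.
2. **p<0.05 must be reached in favour of LYMPHA.** The word comparable then has no effect, and a procedure that is exactly as safe as the control nearly always fails.

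At stake is the protocol's only stated rule for a comparative safety conclusion about an added surgical step. Two analysts could apply it to the same data and reach opposite answers, neither of which would show comparability.

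**Working it through.** **The plan's own figures.** None exists for complications. The only power figures, 56% and 88% in section 12.6.2, are for lymphedema at 30% vs 4%. They reproduce with a two-look z-test, unpooled variance and two-sided 5% Pocock bounds (2.178 at both looks). First stage, 20 per arm: SE = sqrt((0.30×0.70 + 0.04×0.96)/20) = 0.1114; z = 0.26/0.1114 = 2.333; power = Φ(2.333 − 2.178) = 56.2%. Over both stages the power is 88.2%. These figures carry no information about complications.

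**Inputs for the check.**

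- 30 per arm (section 2.4); 40 per arm (20 + 20, section 12.6.2) as an alternative; 43 in A and 44 in C if both phases are pooled (30 + 13 and 30 + 14, sections 2.4 and 3.4).
- Assumed, because the protocol is silent: two-sided Fisher's exact test at 5%, and control complication rates from 5% to 30%.

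**Method.** Let X be the number of complications in C, binomial(n_C, p_C), and Y the number in A, binomial(n_A, p_A). Sum P(X=x)·P(Y=y) over all tables that satisfy the rule, with Fisher's p computed exactly for each table.

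**Reading 1: a non-significant difference counts as comparable.** Chance that a truly doubled rate passes:

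| Control vs LYMPHA | 30 per arm | 40 per arm |
|---|---|---|
| 5 vs 10% | 98% | 96% |
| 10 vs 20% | 90% | 84% |
| 20 vs 40% | 70% | 59% |
| 25 vs 50% | 59% | 44% |
| 30 vs 60% | 44% | 28% |

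Pooling both phases gives 94%, 82%, 53%, 37% and 24% for the same rows. A one-sided 5% test for harm with 30 per arm gives 95%, 84%, 58%, 47% and 34%.

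Two single tables show where the line falls with 30 per arm. Three complications in A against 10 in C give p = 0.057, which passes. Three against 11 give p = 0.03, which fails.

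**Reading 2: p<0.05 in favour of LYMPHA is required.** With 30 per arm and truly equal rates, LYMPHA is significantly lower in 0.5% of trials at 10% and 1.1% at 20%. A doubled rate passes in under 0.1%.

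**What an interval would show.** The 95% half-width for the C−A difference with equal rates p and n per arm is 1.96·sqrt(2p(1−p)/n). With n = 30 and p = 0.10 this is 1.96·sqrt(0.18/30) = 15.2 points. With p = 0.20 it is 20.2 points.

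**What a margin would need.** With equal true rates, one-sided 2.5% and 80% power, n per arm = (1.96 + 0.84)²·2p(1−p)/m². For illustration only, at a 10% rate this gives 142 for m = 10 points and 63 for m = 15. At a 5% rate it gives 34 for m = 15 and 19 for m = 20.

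**The case against.** Several objections carry weight.

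- **A reader might infer that the rule is lenient and that a doubled complication rate would usually pass.** The document does not support that as a flat statement. Section 12.7 does not say that non-significance counts as comparable. Read literally, p<0.05 has to be reached, and a doubled rate then almost never passes. Even on the lenient reading, the result depends on an unstated control rate: with 30 per arm it falls below one half at 30 vs 60%, and with 40 per arm already at 25 vs 50%. The low-risk remark in section 7.1 points towards the lower rates but is not a figure.
- **A reader might infer that the conclusion is fixed whatever the data.** It is not: 3/30 against 11/30 would be flagged.
- **A reader might infer that 30 per arm can never support a claim of comparability.** That depends on the margin and the rate. At a 5% rate and a 20-point margin, 19 per arm would do. Whether so wide a margin is acceptable is a judgement for the sponsor.
- **The test is not stated, and a statistical analysis plan might name one, even a non-inferiority test.** This is fair as to the test. But the protocol itself fixes a success rule with a significance threshold, and that wording cannot be applied as it stands.
- **The reach is limited.** The heading speaks of future studies and the verb is conditional. Complications are not among the objectives in sections 1.1 and 1.2, the outcomes in section 10, or the analyses in sections 12.4 and 12.5. Adverse event reporting and oversight by the monitoring committee (sections 7.2 and 11.2) do not depend on section 12.7. This stands, and it lowers the severity.

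**Conclusion.** The point holds as a defect of the stated rule: section 12.7 cannot be interpreted, because p<0.05 is attached to comparability without a margin. Under one reading a doubled rate passes in 98% to 44% of trials with 30 per arm, and 96% to 28% with 40 per arm, as the control rate runs from 5% to 30%. Under the other, equal safety succeeds in about 1 trial in 100 or fewer at control rates of 10% and 20%. These sizes rest on two assumptions the protocol does not settle: a two-sided Fisher's exact test and the range of complication rates. The defect itself needs neither assumption. The primary efficacy comparison and the 56% and 88% power figures are not affected, so the severity is low.

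**What to change.** In section 12.7, remove p<0.05 from the safety criterion. State that the difference in complication rates, Group C minus Group A, will be reported with its 95% confidence interval. Then choose one of two courses:

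- keep the claim of comparability, and judge it by the upper confidence limit against a margin that the sponsor justifies and fixes before outcome data are reviewed; or
- call the comparison descriptive and make no claim of comparability.

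The cost is a protocol wording change, with no new measurements and no effect on the primary analysis. The descriptive course needs no further patients, but the sponsor gives up a formal safety claim. The margin course requires a check that the planned number per arm can support the chosen margin.
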